### 3.5 Excluded criteria

Data that meets any of the following conditions need to be eliminated:

- (1) Congenital gastrointestinal malformations (e.g., intestinal atresia, Hirschsprung's disease) or spontaneous intestinal perforation;
- (2) Hereditary metabolic disorders;
- (3) Incomplete clinical data or refusal of participation.

### 3.6 Observation items

- (1). Baseline Characteristics: Neonatal demographics (sex, gestational age, birth weight, small for gestational age [SGA] status), maternal factors (mode of delivery, premature rupture of membranes, chorioamnionitis), neonatal birth history (1-min Apgar score  $\leq 7$ , intrauterine distress), and preterm complications (patent ductus arteriosus [PDA], respiratory distress syndrome [RDS], sepsis, shock), feeding pattern, and requirement for mechanical ventilation.

- (2). Laboratory and Clinical Assessment Indicators: Hepatobiliary function:

Albumin, albumin/globulin ratio, total bile acid; Hematologic and inflammatory parameters: White blood cell (WBC), absolute neutrophil (NEU), lymphocyte (LYM), monocyte (MON), eosinophil (EOS) counts, red blood cell (RBC), platelet (PLT) count, mean platelet volume (MPV), platelet distribution width (PDW), C-reactive protein (CRP), neutrophil-to-lymphocyte ratio (NLR), monocyte-to-lymphocyte ratio (MLR), neutrophil-to-monocyte ratio (NMR), systemic inflammatory index (SII), systemic inflammatory response index (SIRI), aggregate inflammatory systemic index (AISI); Metabolic: Serum lactate, blood glucose; Organ dysfunction assessment: Neonatal Sequential Organ Failure Assessment (nSOFA) score.

(3). Primary Outcome Indicators:

- Occurrence of perforated necrotizing enterocolitis (PNEC);
- In-hospital mortality.

(4). Secondary Outcome Indicators:

- Bell's staging of NEC;
- surgical NEC

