immune-inflammatory biomarkers (such as intestinal fatty acid binding protein or albumin) to address this limitation [12,13]. Peripheral blood cell analysis serves as a widely accessible and rapid auxiliary diagnostic tool in neonatal intensive care units (NICUs). Dynamic changes in peripheral white blood cell (WBC) counts and subset distribution have been validated as biomarkers closely associated with NEC [14]. Accumulating evidence underscores the involvement of lactate metabolism in immunomodulation and its influence on disease pathogenesis [15]. However, the combined utility of lactate levels and peripheral WBC profiles for NEC diagnosis and prognostic stratification remains unexplored.

As NEC progresses, particularly in cases of perforated NEC, it can evolve from a localized intestinal disease into a systemic illness characterized by a sepsis-like state and multi-organ dysfunction. The Neonatal Sequential Organ Failure Assessment (nSOFA) score is a validated tool designed to objectively quantify the degree of organ dysfunction in critically ill neonates by evaluating the respiratory, cardiovascular, and hematologic systems [16]. Studies have demonstrated that higher nSOFA scores are strongly and independently associated with mortality risk in neonates with respiratory distress syndrome, late-onset sepsis, and NEC [16-18]. However, single nSOFA lacks sufficient sensitivity for severe NEC subtypes like PNEC-specific risk stratification: while it predicts overall NEC mortality and the need for surgical intervention [16], existing studies have not specifically evaluated its performance in distinguishing NEC from non-perforated NEC or predicting PNEC-related mortality. The Lewis et al. [16] study included surgical NEC (e.g., laparotomy or peritoneal drain placement) but did not isolate PNEC as a distinct endpoint, leaving a critical gap in understanding how nSOFA performs in this highest-risk subgroup.

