### 3.3 data collection

Data collection was performed via structured extraction from electronic medical

records. The following variables were systematically retrieved: (1) Neonatal medical history, including sex, gestational age, birth weight, and history of birth asphyxia (e.g., Apgar scores); (2) Maternal medical history, particularly mode of delivery, chorioamnionitis, and premature rupture of membranes; (3) NEC-related clinical parameters: Bell's staging, clinical manifestations (abdominal distension, bloody stools, pneumoperitoneum), complications (patent ductus arteriosus [PDA], sepsis, shock), therapeutic interventions (mechanical ventilation, surgical treatment), and mortality; (4) CBC parameters, lactate levels, and parameters required for calculating the nSOFA score at the onset of NEC.

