### 3.7 Statistical processing

Statistical analyses and graphic visualization were performed using SPSS 26.0 (IBM Corp.) and GraphPad Prism 9.0. Data for normally distributed, skewed distributed, and categorical variables were expressed as mean  $\pm$  standard deviation, median (interquartile range), and frequency (%), respectively. Intergroup comparisons of categorical variables were conducted using the Chi-square ( $\chi^2$ ) test or Fisher's exact test, while continuous variables were analyzed using the Student's t-test or Mann-Whitney U test. Variables with  $p < 0.05$  in univariate analysis were subsequently included in multivariate logistic regression analysis.

Mediation analysis was performed using the PROCESS macro 4.1, with 1000 bootstrap iterations to decompose the total effect into direct and indirect paths. Receiver operating characteristic (ROC) curve analysis was conducted using SPSS 26.0 to evaluate the predictive performance of individual and combined biomarkers. All analyses adopted two-tailed tests, and  $p < 0.05$  was considered statistically

significant.

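### Sepsis, shock, ventilation and several labs are not timed against NEC onset or perforation, so consequences of perforation can be reported as its predictors

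*Combined protocol and SAP*

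**What the plan says.** Section 3.6, item (1), places among the baseline characteristics "preterm complications (patent ductus arteriosus [PDA], respiratory distress syndrome [RDS], sepsis, shock), feeding pattern, and requirement for mechanical ventilation". Section 3.3, item (3), lists overlapping items as NEC-related clinical parameters: "complications (patent ductus arteriosus [PDA], sepsis, shock), therapeutic interventions (mechanical ventilation, surgical treatment), and mortality". The Abstract repeats the section 3.3 list. None of these places gives a date or window.

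The only timing phrase for any predictor is in section 3.3, item (4). It covers the CBC, lactate and "parameters required for calculating the nSOFA score at the onset of NEC". Onset is not defined there or elsewhere. Section 3.6, item (2), adds labs outside that phrase: "Albumin, albumin/globulin ratio, total bile acid", CRP and blood glucose.

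The first primary outcome in section 3.6 is "Occurrence of perforated necrotizing enterocolitis (PNEC"; the other is in-hospital mortality. Section 3.7 says that variables reaching p < 0.05 "in univariate analysis were subsequently included in multivariate logistic regression analysis". It sets no condition on timing and names no outcome for the model, so a PNEC model is an inference from the outcome list. Section 2 states the aim as finding indicators that predict progression and death.

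**The concern.** A predictor has to precede what it predicts. Section 1.1 describes the opposite direction for organ failure: "As NEC progresses, particularly in cases of perforated NEC, it can evolve from a localized intestinal disease into a systemic illness", with a sepsis-like state and dysfunction of several organs. Sepsis, shock and the need for ventilation may thus be results of perforation in some infants. If they are coded as present or absent over the whole stay and then screened against PNEC, their odds ratios partly describe what perforation does. The estimates for other variables are then adjusted for a consequence of the outcome.

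The labs raise the same question in a weaker form. Section 3.4 accepts pneumoperitoneum as diagnostic evidence, so an infant may already be perforated when NEC is recognised, and a sample tied to onset need not precede perforation. The five undated labs have no anchor at all. At stake is whether results on PNEC can be called prediction, which is what section 2 promises.

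**Working it through.** **1. The passages side by side**

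| Item | Section 3.6 | Section 3.3 | Time point |
|---|---|---|---|
| Sepsis, shock | baseline, preterm complication | NEC-related complication | none |
| Mechanical ventilation | baseline | therapeutic intervention, next to surgery | none |
| CBC, lactate, nSOFA | laboratory and clinical assessment | item (4) | onset of NEC, undefined |
| Albumin, albumin/globulin ratio, bile acid, CRP, glucose | laboratory | not listed | none |
| Time of perforation | not listed | not listed | none |

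The two classifications do not settle the timing. PDA appears in both lists, under both labels, so neither label can be read as a date.

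**2. How large the distortion could be**

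The plan gives no figure to reproduce: 220 is a count, with no PNEC share and no covariate rates. The following is an illustration.

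From the documents: N = 220, two-sided p < 0.05. Assumed: PNEC share 20-50% (44 to 110 infants); shock before perforation in 20% of both groups (true OR 1.0); a further g = 20 points acquired after perforation in PNEC; controls later acquire c × g.

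- p1 = 0.20 + 0.20 = 0.40; p0 = 0.20 + c × 0.20
- OR = [p1/(1 − p1)] / [p0/(1 − p0)]
- Chance of passing the screen = Φ[(p1 − p0 − 1.96 × SE0)/SE1], where SE0 is the pooled and SE1 the unpooled standard error of the difference

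| c | p0 | OR | Chance, PNEC 20-50% |
|---|---|---|---|
| 0.5 | 0.30 | 0.667/0.429 = 1.56 | 25-34% |
| 0 (extreme) | 0.20 | 0.667/0.250 = 2.67 | 77-90% |
| 1 | 0.40 | 1.00 | 5% (the test level) |

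Worked cell, c = 0.5 and 44 PNEC infants: pooled proportion 0.32, SE0 = 0.0786, SE1 = 0.0815; (0.10 − 1.96 × 0.0786)/0.0815 = −0.66; Φ = 0.25.

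If PNEC is allowed up to 80%, the ranges become 22-34% (c = 0.5) and 72-90% (c = 0). The share may be high because section 3.4 requires surgery. That requirement is absent from the Abstract, and section 3.6 lists surgical NEC as an outcome, so the share cannot be fixed from the text.

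**3. Why the cut-off must not depend on perforation**

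One could count these events only if they came before perforation. That shortens the exposure window for PNEC infants alone. Assume shock at time zero in 20% of both groups, half of the PNEC infants already perforated, and half of the shock in those infants beginning after perforation. Coded prevalence in PNEC is 0.5 × 20% + 0.5 × 10% = 15%, against 20% in controls. OR = (0.15/0.85)/(0.20/0.80) = 0.71, a spurious protective effect. If all of that shock began after perforation, prevalence is 10% and OR = 0.44.

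**The case against.** The strongest reply is that the central predictors are already timed. Section 1.2 names lactate, CBC and nSOFA as the measures to be integrated, and section 3.3 ties them to NEC onset. Section 3.7 limits the ROC analysis to individual and combined biomarkers, so sepsis, shock and ventilation are not stated inputs to any AUC. This stands: the clinical items affect the odds ratios and adjustment, and only the lab gap can reach the AUC.

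Second, part of the timed information may already be in hand. Section 1.1 says nSOFA covers the respiratory and cardiovascular systems, so its onset parameters may overlap with ventilation and shock. This also stands, and the fix uses it.

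Third, the words used in section 3.6 favour a reading before onset. That is possible, but section 3.3 points the other way and an extractor is not told which applies.

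Fourth, section 1.1 says NEC in general can become systemic, so controls would acquire shock too. That is why the half-rate case leads and the zero-rate case is marked extreme.

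Finally, separating perforated from non-perforated NEC is a legitimate aim. Section 1.1 gives the gap as "distinguishing NEC from non-perforated NEC or predicting PNEC-related mortality"; reading its first part as perforated against non-perforated NEC is an inference. That aim is discrimination, and should be reported as such.

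**Conclusion.** The point holds as an omission with a plausible direction of bias, and it should be corrected. The plan as written permits consequences of perforation to be reported as predictors of a primary outcome, and contains no rule to stop it.

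A reader might infer more: that such variables did enter the model, or that the biomarker AUCs are inflated by shock or sepsis. The documents support neither. They give no timing data, no share of infants perforated at onset or at sampling, and no ROC analysis of the clinical items. Nor should the lab gap be extended to all labs as undated, since CBC, lactate and nSOFA carry an onset anchor, though an undefined one.

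The size is unknown. The illustration runs from no distortion, through an OR of 1.6 (25-34% chance of passing the screen), to 2.7 (77-90%). It rests wholly on assumed rates and covers the univariate screen only, not the adjusted model. It concerns the PNEC model; no separate illustration is offered for mortality.

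**What to change.** - Reconcile sections 3.3 and 3.6 on what sepsis, shock and ventilation represent.
- Define NEC onset as one time zero.
- For every infant, whatever the outcome, count sepsis, shock and ventilation as candidate predictors only if present at or before time zero. Where they suffice, use the onset-timed nSOFA parameters already collected.
- Take every lab in section 3.6 from one stated window around time zero, the same for all infants, so that old values are not admitted and onset samples are not lost.
- Do not use a perforation-dependent cut-off in the main analysis.
- Flag infants already perforated at time zero or at lab sampling. Describe PNEC results that include them as discrimination of perforated from non-perforated NEC.
- Repeat the PNEC odds ratios and AUC without those infants as a sensitivity analysis, and rest any claim of prediction on it.

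**Cost.** Onset dates, sampling times and the first sign of perforation must come from the same electronic records. Some will probably be missing. Section 5 ends case collection in March 2025, so a second extraction may be needed. The sensitivity analysis has fewer events: with PNEC assumed at 20-80% of 220 (44-176 events), 22-88 remain if half were already perforated, and 11-44 if three quarters were. It may be imprecise, which is why it is not proposed as the main analysis.

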### 3.7 Statistical processing

Statistical analyses and graphic visualization were performed using SPSS 26.0 (IBM Corp.) and GraphPad Prism 9.0. Data for normally distributed, skewed distributed, and categorical variables were expressed as mean  $\pm$  standard deviation, median (interquartile range), and frequency (%), respectively. Intergroup comparisons of categorical variables were conducted using the Chi-square ( $\chi^2$ ) test or Fisher's exact test, while continuous variables were analyzed using the Student's t-test or Mann-Whitney U test. Variables with  $p < 0.05$  in univariate analysis were subsequently included in multivariate logistic regression analysis.

Mediation analysis was performed using the PROCESS macro 4.1, with 1000 bootstrap iterations to decompose the total effect into direct and indirect paths. Receiver operating characteristic (ROC) curve analysis was conducted using SPSS 26.0 to evaluate the predictive performance of individual and combined biomarkers. All analyses adopted two-tailed tests, and  $p < 0.05$  was considered statistically

significant.

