Statistical processing	Statistical analyses and graphic visualization were performed using SPSS 26.0 (IBM Corp.) and GraphPad Prism 9.0. Data for normally distributed, skewed distributed, and categorical variables were expressed as mean $\pm$ standard deviation, median (interquartile range), and frequency (%), respectively. Intergroup comparisons of categorical variables were conducted using the Chi-square ( $\chi^2$ ) test or Fisher's exact test, while continuous variables were analyzed using the Student's t-test or Mann-Whitney U test. Variables with $p < 0.05$ in univariate analysis were subsequently included in multivariate logistic regression analysis.  Mediation analysis was performed using the PROCESS macro 4.1, with 1000 bootstrap iterations to decompose the total effect into direct and indirect paths. Receiver operating characteristic (ROC) curve analysis was conducted using SPSS 26.0 to evaluate the predictive performance of individual and combined biomarkers. All analyses adopted two-tailed tests, and $p < 0.05$ was considered statistically significant.
Abbreviation	NEC, necrotizing enterocolitis; PNEC, perforated necrotizing

enterocolitis; VLBW, very low birth weight; SGA, small for gestational age; NICUs, neonatal intensive care units; PDA, patent ductus arteriosus; RDS, Respiratory distress syndrome; CRP, C-reactive protein; WBC, white blood cell; CBC, complete blood count; NEU, absolute neutrophil count; LYM, absolute lymphocyte count; MON, absolute monocyte count; EOS, eosinophilic granulocyte; RBC: red blood cell; PLT, platelet count; MPV, mean platelet volume; PDW, platelet distribution width; NLR, neutrophil-to-lymphocyte ratio; NMR, neutrophil-to-monocyte ratio; MLR, monocyte-to-lymphocyte ratio; SII, systemic inflammatory index =  $(NEU*PLT)/LYM$ ; SIRI, systemic inflammatory response index =  $(NEU*MON)/LYM$ ; AISI, aggregate inflammatory systemic index =  $(NEU*MON*PLT)/LYM$ ; nSOFA, neonatal sequential organ failure assessment; ROC, receiver operating characteristic; AUC, the area under the ROC curve; OR, odds ratio; CIs, confidence intervals.

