## 1. project basis

### 1.1 Research background

Necrotizing enterocolitis (NEC), a life-threatening gastrointestinal disorder predominantly, affects 5–12% of very low birth weight (VLBW) neonates, with 20–40% of cases progressing to severe disease requiring surgical intervention, while survivors often endure lifelong consequences, including short-bowel syndrome and neurodevelopmental impairments [1-4]. Despite advances in neonatal care, early identification of high-risk patients remains challenging due to the nonspecificity of clinical signs (e.g., abdominal distension, feeding intolerance) and radiographic findings (e.g., pneumatosis intestinalis), which frequently manifest only after irreversible bowel damage has occurred [5]. Furthermore, current diagnostic tools or conventional biomarkers lack both sensitivity and specificity for early risk stratification of NEC, underscoring an urgent need for biomarkers that integrate pathophysiological mechanisms to guide preemptive therapeutic strategies.

Emerging evidence underscores the multifactorial pathophysiology of NEC, where intestinal ischemia-reperfusion injury, exaggerated immune activation, and microbial dysbiosis converge to drive disease progression [6]. Hypoxic-ischemic injury constitutes a key pathological mechanism underlying intestinal mucosal damage in NEC, driving dysregulation of cellular processes including apoptosis, autophagy, proliferation, and migration within intestinal tissues [7]. In infants with NEC, persistent hypoxemia and compromised tissue perfusion induce metabolic reprogramming, marked by a shift toward glycolytic dominance—a compensatory adaptation to oxygen deprivation. Within this framework, serum lactate, as a well-established marker of tissue hypoperfusion and anaerobic metabolism, has garnered attention for its prognostic relevance. Elevated lactate levels correlate with transmural intestinal necrosis and predict fatal outcomes in NEC, reflecting the severity of ischemic insult [8,9]. However, lactate alone lacks specificity, as hyperlactatemia may arise from concurrent sepsis or perinatal asphyxia, limiting its standalone utility [10,11]. Recent studies propose combining lactate with

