### 3.2 Sample size

220 newborns who suffered from necrotizing enterocolitis between July 1, 2017 to December 31, 2022.

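### Student's t-test is named with no provision for unequal variances, so the p<0.05 screen can be miscalibrated for t-tested markers if group sizes and SDs both differ; Welch's test is a cheap improvement

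*Combined protocol and SAP*

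**What the plan says.** Section 3.7 gives the two-group comparisons: "continuous variables were analyzed using the Student's t-test or Mann-Whitney U test". The Abstract repeats this. Neither place mentions Welch's test, a variance check or a rule for unequal variances. The choice between the two tests is not spelled out either. Because the summary statistics are split by normal and skewed distribution, the natural reading is that normally distributed variables go to the t-test and skewed ones to Mann-Whitney.

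The p-value is then used for selection. The Abstract says: "Variables with $p < 0.05$ in univariate analysis were subsequently included in multivariate logistic regression analysis". Section 3.7 has the same rule, and it is the only entry rule stated. Section 3.7 also fixes the sidedness: "All analyses adopted two-tailed tests".

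The groups come from the two primary outcomes in section 3.6, perforated NEC and "In-hospital mortality". Section 3.2 gives the total as "220 newborns who suffered from necrotizing enterocolitis between July 1, 2017 to December 31, 2022", with no expected number of perforations or deaths. No SDs are given anywhere.

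**The concern.** Student's t-test in its usual form pools the two variances. That does no harm when the groups are of equal size or when their SDs are equal. When both differ, the pooled standard error is wrong. It is too small if the smaller group is the more variable, and too large if the smaller group is the less variable.

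Here the groups are whatever the outcomes make them, so an even split is not secured for either primary outcome. The p-value also decides which normally distributed markers reach the multivariable model. A miscalibrated test of mean difference can therefore misstate the reported univariate evidence and, in the conservative direction, can keep out a marker whose mean really differs.

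**Working it through.** The plan has no power or error-rate calculation to reproduce. The check is of the actual two-sided error rate of the named test at a nominal 5%.

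**Inputs from the documents:** total N = 220 (section 3.2); two-sided 0.05 threshold (section 3.7 and Abstract).

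**Assumed inputs, not in the documents:** smaller group of 22, 44, 66, 88 or 110 infants; SD ratio r (smaller group to larger group) from 0.5 to 2; normal data.

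**Large-sample formula.** Set the larger group's SD to 1, with n1 the smaller group and n2 the larger.

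- Variance of the mean difference as the pooled test estimates it: V_pool = [((n1−1)r² + (n2−1)) / 218] × (1/n1 + 1/n2)
- True variance: V_true = r²/n1 + 1/n2
- Actual error rate ≈ 2 × [1 − Φ(1.971 × √(V_pool/V_true))], where 1.971 is the t critical value on 218 df

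**44/176, r = 2.** V_pool = (43×4 + 175)/218 × (1/44 + 1/176) = 1.592 × 0.02841 = 0.0452. V_true = 4/44 + 1/176 = 0.0966. The ratio is 0.468 and its root 0.684. Then 1.971 × 0.684 = 1.349, so the error rate is about 17.7%.

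**44/176, r = 0.67.** V_pool = 0.8913 × 0.02841 = 0.0253. V_true = 0.4489/44 + 1/176 = 0.0159. The ratio is 1.594 and its root 1.263. Then 1.971 × 1.263 = 2.488, so the error rate is about 1.3%.

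**110/110, any r.** V_pool and V_true both equal (r² + 1)/110, so the ratio is 1 and the error rate stays at about 5%.

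**Simulation** (100,000 normal datasets per cell, no difference in means), error rate of Student's test in %:

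| Split | r = 0.5 | r = 0.67 | r = 1 | r = 1.5 | r = 2 |
|---|---|---|---|---|---|
| 22/198 | 0.1 | 0.8 | 5.1 | 15.3 | 24.7 |
| 44/176 | 0.5 | 1.4 | 5.0 | 12.3 | 18.0 |
| 66/154 | 1.3 | 2.1 | 5.0 | 9.5 | 12.5 |
| 88/132 | 2.7 | 3.5 | 4.9 | 7.1 | 8.3 |
| 110/110 | 5.1 | 5.0 | 5.1 | 5.0 | 5.1 |

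Welch's test stayed between 4.9% and 5.2% in every cell.

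**Power in the conservative direction.** Take 44/176, r = 0.67 and a true mean difference of 0.4 SD of the larger group. The true standard error is √0.0159 = 0.126.

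- Student needs a difference above 1.971 × √0.0253 = 0.314, so power ≈ Φ((0.400 − 0.314)/0.126), about 75%.
- Welch, on about 97 df (critical value 1.985), needs a difference above 0.250, so power ≈ Φ((0.400 − 0.250)/0.126), about 88%.

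Simulation gives the same two figures.

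**Price of Welch when SDs are equal.** Simulated power at a difference of 0.5 SD is 84.1% with Student and 83.1% with Welch at 44/176, and 60.8% and 57.8% at 22/198. The loss is about 1 and 3 percentage points.

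**The case against.** **The split and the SDs are not in the documents.** This stands. No proportion of perforations or deaths is given. The background figure, "with 20–40% of cases progressing to severe disease requiring surgical intervention", is neither. Section 3.4 admits only infants who had surgery, so that figure cannot indicate the split within the cohort. Perforation could be near half, and then unequal spread does no harm.

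**The plan never says that the variances are pooled.** True: that is the usual meaning of Student's test, not the plan's wording. Standard software may print the unequal-variance result alongside, but the plan does not say that this result would be used. Leaving the choice open until the output is seen is not a safeguard.

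**A reader might infer that noise markers flood into the model.** The documents and the arithmetic do not support this. A marker unrelated to outcome has the same distribution, and so the same variance, in both groups, and Student's error rate is then about 5% at every split. The inflated rates apply to a marker with equal means but different spread. Such a marker is related to outcome, though not through its mean.

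**A reader might also infer that the whole screen has a wrong error rate.** That goes too far. Categorical variables use chi-square or Fisher tests, and skewed ones presumably use Mann-Whitney. Several section 3.6 markers are ratios or products of counts and may well be skewed. How many variables reach the t-test is unknown. Mann-Whitney has its own distortion under unequal spread (about 1.6% to 11.0% at 44/176 for ratios of 0.5 to 2), which this point neither covers nor cures.

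**Conclusion.** The point holds as a conditional one. The plan names Student's t-test, makes no provision for unequal variances, and lets the p-value decide entry to the logistic model. If group sizes and SDs both differ, the test of mean difference is miscalibrated for the variables sent to it. The distortion is modest at 88/132, larger at 44/176, and absent with equal groups or equal SDs. Its direction depends on which group is the more variable. Every figure rests on an assumed split, an assumed SD ratio and normal data.

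It is not shown that any reported p-value will be wrong, and no effect on the final model or its AUC has been quantified. This is a cheap improvement in method. It does not address the wider weaknesses of selecting variables by univariate p-values.

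**What to change.** In section 3.7 and in the Abstract, replace Student's t-test with Welch's unequal-variance t-test for normally distributed continuous variables. State that it is used for all of them, without a preliminary variance test. In the screening rule, use the Welch p-value for those variables only; the chi-square, Fisher and Mann-Whitney p-values stay as they are.

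This is a wording change in two places and needs no new data. The downside is about 1 to 3 percentage points of power if the variances are truly equal.

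### The entry rule for the multivariable model lets the blood-count indices, and by inference nSOFA, enter beside their own components, which makes marker-level odds ratios imprecise and selection unstable

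*Combined protocol and SAP*

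**What the plan says.** Section 3.7 (repeated in the Abstract) compares groups one variable at a time. Variables with p<0.05 "in univariate analysis were subsequently included in multivariate logistic regression analysis". The plan gives no other selection rule, no entry method, no number of models and no collinearity check. Section 3.1 names correlation analysis but gives it no role in choosing variables.

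The candidates come from section 3.6. That list contains:

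- WBC, then "absolute neutrophil (NEU), lymphocyte (LYM), monocyte (MON), eosinophil (EOS) counts", and the platelet count;
- six indices: NLR, MLR, NMR, SII, SIRI and AISI;
- "Organ dysfunction assessment: Neonatal Sequential Organ Failure Assessment (nSOFA) score";
- shock and the need for mechanical ventilation, among the baseline characteristics.

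The abbreviation list in the Abstract gives formulas for SII, SIRI and AISI in terms of NEU, MON, PLT and LYM. It names NLR, NMR and MLR as ratios of the same counts. Section 1.1 says that nSOFA quantifies organ dysfunction "by evaluating the respiratory, cardiovascular, and hematologic systems". The individual scored items are not listed.

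**The concern.** An odds ratio from a multivariable model describes a change in one variable with the others held fixed. If an index sits beside the counts it is computed from, its coefficient describes only what is left of the index once its parts are fixed. If nSOFA sits beside ventilation, shock and platelets, its coefficient describes the score at fixed values of variables from the same three organ systems. Neither is the effect of the whole index or score as it would be used at the bedside.

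This matters because the study wants more than a prediction. Section 3.1 aims to single out biomarkers and to inform the mechanisms of progression. Section 1.2 presents lactate, blood count and nSOFA as complementing one another. Both aims require odds ratios to be read marker by marker. With heavy overlap, chance can decide which marker keeps p<0.05, and a marker that truly drives risk can lose significance.

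**Working it through.** The plan has no figure to reproduce. The 220 in section 3.2 is a case count without event rate, effect size or power, and the numbers of perforated cases and deaths are not given. Event rates of 15%, 25% and 40% are assumed below.

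**1. Overlap among the count variables (from the plan's definitions, no assumptions).** On the log scale:

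- NLR = NEU − LYM
- MLR = MON − LYM
- NMR = NEU − MON
- SII = NEU + PLT − LYM
- SIRI = NEU + MON − LYM
- AISI = NEU + MON + PLT − LYM

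All six are exact linear combinations of four counts, so the ten variables have rank 4. Links among the indices follow, for example AISI = SIRI × PLT and SII = NLR × PLT. WBC, listed beside its own subset counts, adds further overlap.

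**2. Raw scale.** Here the rank is 10 and the model can be fitted. VIFs were simulated with n=220, lognormal counts, log-SD 0.3 to 0.9 and correlation 0 or 0.3 (all assumed). Ranges of the median VIF with all ten variables in the model:

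| Variable | Median VIF |
|---|---|
| NLR | 5.7–60.2 |
| SII | 7.5–55.4 |
| SIRI | 10.4–75.6 |
| AISI | 8.7–50.9 |
| NEU | 3.1–23.8 |
| LYM | 1.3–9.1 |

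**3. Is joint entry likely?** If NLR drives the outcome (assumed 0.6 log-odds per log unit), NLR and at least one of NEU or LYM pass the p<0.05 screen in 60%, 77% and 88% of runs at 15%, 25% and 40% events.

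**4. nSOFA.** Assumptions: a score summed from respiratory, cardiovascular and platelet bands; risk driven only by the total, at 0.2 log-odds per point; n=220. nSOFA plus at least one of ventilation, shock and platelets passes the screen in 90%, 97% and 99% of runs. All four pass in 29%, 46% and 47%. With all three items (platelets as a log) put in the model:

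| Events | SE, nSOFA alone | SE, with items | Ratio | p<0.05, alone | p<0.05, with items |
|---|---|---|---|---|---|
| 15% | 0.051 | 0.098 | 1.92 | 97% | 53% |
| 25% | 0.044 | 0.086 | 1.95 | 100% | 70% |
| 40% | 0.043 | 0.082 | 1.91 | 100% | 78% |

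The VIF for nSOFA is about 3.95, and √3.95 = 1.99 agrees with the SE ratios. The median coefficient with the items is 0.206 to 0.211 against a true 0.2, so there is no material bias. At 15% events the typical z falls from 0.200/0.051 = 3.9 to 0.206/0.098 = 2.1, barely above 1.96.

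**5. Sensitivity to the effect size.** At 15% events with all items in the model, nSOFA reaches p<0.05 in 33%, 55%, 71% and 84% of runs for 0.15, 0.20, 0.25 and 0.30 log-odds per point.

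**6. Effect on discrimination.** At 15% events and 0.2 per point, adding the items moves the AUC in new data from 0.68 to 0.66 and the apparent AUC from 0.68 to 0.70. This is modest overfitting.

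**The case against.** The strongest reply is that collinearity costs precision and does not invalidate the model. Coefficients are estimated jointly, so a redundant covariate does not count the same fact twice. The conditional odds ratio has a defined meaning, the nSOFA coefficient was not materially biased, and discrimination hardly changed. All of this stands. A reader might infer that the results would be uninterpretable, and the calculations do not support that.

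Joint entry also depends on the univariate screen, and the plan does not say that there will be a single model; there are two primary outcomes. So overlapping variables can enter together, but it is not certain that they will.

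A reader might also conclude from the rank of 4 that the model cannot be fitted. That would need all ten variables to pass the screen and to enter log-transformed, and the plan specifies no transformation.

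The documents do not show that nSOFA is built from platelet count, ventilation and shock. They name three organ systems; shock appears only as a complication. The nSOFA overlap is therefore an inference, weaker than the overlap that the count definitions prove. Nor does the plan promise to label its own findings as independent predictors: its wording about independent association in section 1.1 describes earlier studies.

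These replies limit the point but do not remove it. No section separates an index from its components, and the correlation analysis is not tied to selection.

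**Conclusion.** The point holds as a weakness in a stated rule. Followed as written, section 3.7 can put an index or score in the same model as its components. The resulting odds ratios would be imprecise and would no longer describe the whole index or score, and which marker remains significant would be unstable.

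For the count indices the overlap follows from the plan's own definitions; the size of the VIFs rests on assumed distributions. For nSOFA both the overlap at item level and the loss (standard error nearly doubled, chance of p<0.05 down to about 53–78%) rest on an assumed score structure, an assumed effect of 0.2 per point, event rates of 15–40% and entry of all three items. Reading the plan as producing a biased nSOFA effect or an invalid combined ROC model would go too far. This is a worthwhile and cheap improvement, and it does not invalidate the study.

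**What to change.** Add a paragraph to section 3.7, fixed before analysis, for the multivariable step:

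- **nSOFA.** Enter either the total score or the overlapping items (platelet count, mechanical ventilation, shock), not both in one model. Report the alternative as a sensitivity model.
- **Blood counts.** Enter either the raw counts or one index named in advance (for example NLR). Never enter an index with its own components, and do not enter total WBC with all its subsets.
- **Collinearity check.** Report VIFs for each multivariable model, including for any platelet-based index (SII, AISI) kept beside nSOFA. Nothing calculated here justifies barring those indices outright.

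The cost is one paragraph and one extra model. Section 3.3 already collects the data needed for nSOFA, so no new extraction is required. The downside is that some markers significant in the univariate step will be reported univariately only.
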